### **7.6.1 Deaths**

- **Summary:**

All deaths during the study and within 30 days after the last dose of BMS-986158 monotherapy will be summarized for causes of death by schedule.

- **Listing:**

All recorded deaths for All Enrolled subjects will be listed.

### **7.6.2 Serious Adverse Events**

- Overall summary of SAEs and treatment-related SAEs by worst CTC grade will be presented by SOC/PT. By- participant SAE listing will be provided for the All Enrolled population.

- **Summary:**

- Overall summary of SAEs by worst CTC grade (grade 1, 2, 3, 4, 3-4, 5, unknown) presented by SOC/PT

- Overall summary of treatment-related SAEs by worst CTC grade (Grade 1, 2, 3, 4, 3-4, 5) presented by SOC/PT

- **Listing:**

A by-subject SAE listing will be provided for the All Enrolled population.

### **7.6.3 Adverse Events Leading to Discontinuation of Study Therapy**

Adverse events leading to study drug discontinuation are AEs with action taken classification of “Drug was discontinued”. Overall summary of AEs leading to discontinuation and treatment-related AEs leading to discontinuation by worst CTC grade will be presented by SOC/PT. By-participant AEs leading to discontinuation listing will be provided.

**Summary:**

- Overall summary of AEs leading to discontinuation by worst CTC grade (grade 1, 2, 3, 4, 3-4, 5, unknown) presented by SOC/PT

- Overall summary of treatment-related AEs leading to discontinuation by worst CTC grade (any grade, grade 3-4, grade 5) presented by SOC/PT.

- **Listing:**

- A by-participant AEs leading to discontinuation listing will be provided.

#### **7.6.4 Adverse Events Leading to Dose Modification or Delay**

AEs leading to dose delay/reduction/interruption will be summarized by treatment and overall if sufficient data are available.

##### **Summary:**

- Overall summary of AEs leading to dose reduction by worst CTC grade (grade 1, 2, 3, 4, 3-4, 5, unknown) presented by SOC/PT.
- **Listing:**
- A by-subject listing of AEs leading to dose delay/reduction/interruption will be provided.

#### **7.6.5 Overall Adverse Events**

- AEs and drug-related AEs will be tabulated by descending frequency of SOC and descending frequency of PT within each SOC.

##### **Summary:**

- Overall summary of any AEs by worst CTC grade (grade 1, 2, 3, 4, 3-4, 5, unknown) presented by SOC/PT
- Overall summary of treatment-related AEs by worst CTC grade (grade 1, 2, 3, 4, 3-4, 5) presented by SOC/PT.
- Overall summary of AEs occurring in at least 5% of subjects across treatments. This table will be restricted to events with an incidence greater or equal to 5% in any treatment group.
- Overall summary of non-serious AEs presented by SC/PT. This table will be restricted to events with an incidence greater or equal to 5% in any treatment group.
- **Listing:**
- All recorded Adverse Events occurring in the screening, on-treatment, and clinical follow-up periods will be listed.

#### **7.6.6 Multiple Events**

Analyses that take into account the multiple occurrences of a given adverse event will be conducted. In order to prepare these analyses, the CRF data will be processed according to standard BMS algorithms in order to collapse adverse event records into unique records based on the preferred term. This data will be presented as the rate per 100 subject-years of exposure. This analysis will take into account all on-treatment events (allowing more than 1 event per subject) and the total duration of exposure. The subject-years exposure will be computed as the sum over the subjects' exposure expressed in years where the duration of exposure is defined as:

- Date of last dose of study treatment - date of first dose of study treatment + 30+1 days, for subject who are off study treatment and were followed at least 30 days after last dose of study medication. Units for this calculation are subject-days.
- Last known date alive - date of first dose of study medication +1, for subjects who are still on-treatment or who are off study treatment and were followed less than 30 days after last dose of study medication. Units for this calculation are subject-days.

- Subject-years are defined as the sum of subject-days divided by 365.25 and are rounded to a single decimal place of precision.

**Summary:**

The following summary tables will be provided by treatment and overall and may also be provided by schedule.

- Total number and rate (exposure adjusted, i.e., patient-year event rate) of occurrences for all AEs

**Listing:**

- Unique instances of all AEs, i.e., after duplicates have been eliminated and overlapping and contiguous occurrences of the same event (i.e., having the same PT) have been collapsed into the worst severity observed.

### **7.6.7 Clinical Laboratory Evaluations**

Clinical laboratory data will be analyzed using International System of Units (SI). Analyses will be repeated using US conventional units.

**Summary:**

The number (%) of subjects with the following will be summarized by treatment and overall, if appropriate, using the worst CTC grade on-treatment per subject.

- Post-baseline grade
- Grade change from baseline
- Descriptive statistics of laboratory test result and their changes from baseline

**Listing:**

A by-subject listing of these laboratory parameters will be provided. Laboratory abnormality criteria and laboratory results outside of normal range will be listed.

#### **7.6.7.1 Abnormal Hepatic Test**

**Summary:**

The number of subjects with the following laboratory abnormalities from on-treatment evaluations will be summarized by treatment:

- ALT or AST > 3 x ULN, > 5 x ULN, > 10 x ULN and > 20 x ULN
- Total bilirubin > 2 x ULN
- Concurrent (within 1 day) ALT or AST > 3 x ULN and total bilirubin > 2 x ULN
- Concurrent (within 30 days) ALT or AST > 3 x ULN and total bilirubin > 2 x ULN

**Figure:**

- Scatter plot of Total bilirubin peak vs. AST peak
- Scatter plot of Total bilirubin peak vs. ALT peak

On-treatment peak total bilirubin and on-treatment peak AST/ALT within 30 days of liver testing will be plotted.

**Listing:**

A by-subject listing of these specific abnormalities will be provided.

**7.6.8 Vital Signs, and Other Safety Evaluation**

**Summary:**

Vital sign measurements will be summarized by treatment.

- Vital signs summary and changes from baseline

**Listing:**

- Vital signs
- Echocardiogram measurements and findings
- Physical examination findings

**7.6.9 DLT information**

Available DLT data as per the database will be listed.

**7.7 Pharmacokinetics**

All available plasma/serum concentration-time data from participants who receive BMS-986158 will be reported. The Pharmacokinetic (PK) population will be used for all listings. Evaluable PK population will be used for summaries and statistical analyses. Only Part 1 participants will be summarized unless there are more than 5 participants in Part 2.

**7.7.1 Pharmacokinetic Concentrations**

Participant concentration-time profiles will be listed and summarized by treatment and nominal collection time for BMS-986158 and Metabolite BMT-161485. Plot of individual concentration profiles over time will be provided. Plots of mean (+SD) concentration profiles versus time will be presented by treatment (ie, dose schedule, dose and visit) on the same plot. The concentration-time data will be handled by CPAR&O group.

**7.7.2 Pharmacokinetic Parameters**

PK parameters for plasma concentrations from subjects who receive BMS-986158 will be calculated using non-compartmental analysis. All available plasma concentration-time data from subjects who receive BMS-986158 will be reported. All available derived PK parameter values will be included in the PK dataset and reported, but only subjects with adequate PK profiles will be included in summary statistics and statistical analysis.

PK parameters will be provided separately for parent compound BMS-986158 and Metabolite BMT-161485. In general, summary statistics will be tabulated for the pharmacokinetics parameters by dose schedule, dose and visit for each select analyte. To assess the attainment of steady state, geometric mean Ctrough values will be plotted versus study day by dose schedule and dose.

Effective plasma half life, T-HALFeff will be calculated for Accumulation Index (AI) values of AUC(0-24). The formula is as shown in [Figure 7.7.2-1](#) below.

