1.4.4 Clinical Pharmacology and Safety

The current study is a first-in-human study.

At the time of the clinical data cutoff date of 21-Dec-2018, a total of 81 subjects had received at least 1 dose of BMS-986158 in Part 1 of the study under Schedule A, Schedule B or Schedule C. Each subject was administered a single dose of BMS-986158 on Cycle 1 Day 1 (4- to 7-day cycle), and no additional doses were administered until Cycle 2 Day 1. On Cycle 2 Day 1 and each subsequent cycle, subjects in Schedule A received once daily (QD) dosing for 5 consecutive days, followed by a 2-day rest period repeated weekly on a 28-day cycle. Subjects in Schedule B received QD dosing for 14 consecutive days, followed by a 7-day rest period on a 21-day cycle and subjects in Schedule A, a total of 44 subjects have received QD dosing of 0.75 mg

(n=5), 1.25 mg (n=4), 2 mg (n=13), 3 mg (n=10), or 4.5 mg (n=12) BMS-986158. In Schedule B, 8 subjects have received QD dosing of 2 mg (n=4), 3 mg (n=4). In Schedule C, 29 subjects have received QD dosing of 2 mg (n=6), 3 mg (n=12) or 4.5 mg (n=11) BMS-986158. All clinical data are preliminary and subject to change.

As of 21-Dec-2018, a total of 79 subjects (97.5%) experienced at least 1 AE. The most frequent AEs (occurring in \geq 20% of subjects) were diarrhea (49 [60.5%] subjects), nausea (43 [53.1%] subjects), fatigue (41 [50.6%] subjects), decreased appetite (34 [42.0%] subjects), vomiting (34 [42.0%] subjects), thrombocytopenia (32 [39.5%] subjects), dyspnoea (23 [28.4%] subjects), anemia (19 [23.5%] subjects), constipation (19 [23.5%] subjects), and cough (17 [21.0%] subjects). A total of 49 subjects (60.5%) experienced Grade 3 to 4 AEs. Five subjects (6.2%) experienced Grade 5 AEs, all assessed by both Sponsor and investigator to be not related to BMS-986158.

Adverse events evaluated as related to BMS-986158 were experienced by 59 of 81 subjects (72.8%). Thirty-four subjects (42%) experienced diarrhea with none experiencing Grade 3 to 4 diarrhea. Thirty subjects (37%) experienced treatment-related thrombocytopenia including 17 subjects (21.0%) with either Grade 3 or 4 events. Thirteen subjects (16%) were reported to have nausea, including 1 (1.2%) Grade 3 nausea. Other Grade 3 to 4 treatment-related AEs include anemia (3 [3.7%] subjects), vomiting, fatigue, increased bilirubin (2 [2.5%] subjects each), and neutropenia and vertigo (1 [1.2%] subject each). There were no treatment-related AE's of Grade 5 reported.

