In the pivotal 1-month oral toxicity studies, the highest non-severely toxic dose (HNSTD) in dogs was 0.15 mg/kg. The dog was considered the most appropriate species for calculation of the maximum recommended starting dose (MRSD) because a nontolerated dose was attained in dog but not rat and the toxicity profile was similar in both species. The starting dose of 0.75 mg/day was selected based upon the human equivalent dose (HED; scaled by body-surface area) of the HNSTD in dogs (the more sensitive species between dogs and rats) with a safety factor of 1/6. The projected human efficacious dose is estimated to be 2 mg/day.

To assure safety of human subjects, the initial dose of BMS-986158 tested in this study was 0.75 mg/day. Part 1 of this study also evaluates different administration schedules: monotherapy given 5 consecutive days on with 2 days off each week of a 4-week cycle (Schedule A of Part 1); monotherapy given 14 consecutive days on with 7 days off of a 3-week cycle (Schedule B of Part 1); and monotherapy given 7 days on and 14 days off of a 3-week cycle (Schedule C of Part 1). The rationale for the 3 schedules is based on the human half-life of 39 hours. Schedule A effectively provides continuous drug exposure, while Schedules B and C provide intermittent exposure with a break to allow for platelet recovery as needed at higher doses in human trials of other compounds in this class.

For Part 2, Schedule A, has been selected considering the safety, [REDACTED] and PK obtained during Part 1. In addition to adult subjects, adolescent subjects will be included in Part 2.

The increment in the dose levels used in dose escalation especially in the first schedule tested (Schedule A), will be guided by the modified Fibonacci to help mitigate the potential risk inherent in the steep dose/toxicity curve and/or the low therapeutic index seen in preclinical studies. Dose escalation decisions will utilize a modified toxicity probability interval (mTPI) design. Rationale for selection of an mTPI over a 3+3 design includes a more accurate determination of MTD, provides flexibility in cohort size, and allows de-escalation and re-escalation to a previously tried dose. The design provides a simple dose escalation decision algorithm, and in addition to the higher accuracy of MTD selection, it treats fewer subjects at suboptimal doses.

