## 2 STUDY DESCRIPTION

### 2.1 Study Design

This is a phase 1/2a, open label study to characterize the safety and tolerability of BMS-986158 monotherapy in subjects with advanced solid tumors and hematologic malignancies. The study has two segments Part 1 (Phase 1 study - dose escalation, with Schedules A, B and C enrolling at different dosing schedules) and Part 2 (Initial Expansion including subjects with a limited set of tumor types) (see [Figure 2.1-1](#)). In Part 1 and Part 2, BMS-986158 will be studied as monotherapy.

In Part 1, the continuous dosing Schedule A enrolled first. Each subject in Schedules A, B and C of Part 1 is administered a single dose of BMS-986158 on Cycle 1 Day 1 and no additional doses are administered until Cycle 2 Day 1. For subjects in Schedule A on Cycle 2 Day 1, and on each subsequent cycle, subjects receive QD dosing for 5 consecutive days of each week, followed by a 2-day rest period, on a 28-day cycle. For subjects in Schedule B on Cycle 2 Day 1, and on each subsequent cycle, subjects receive QD dosing for 14 consecutive days, followed by a 7-day rest period, on a 21-day cycle. For subjects in Schedule C on Cycle 2 Day 1, and on each subsequent cycle, subjects receive QD dosing for 7 consecutive days, followed by a 14-day rest period, on a 21-day cycle.

[figure not shown]
In Part 2, Schedule A for BMS-986158 administration has been selected for expansion of the 4.5 mg dose, which will be administered for 2 weeks (10 doses) followed by 3.75 mg for the remainder of the treatment period. Adult and adolescent subjects weighing  $\geq 40$  kg will be

administered a flat dose of BMS-986158. Using Schedule A with a loading period of 2 weeks at 4.5 mg followed by 3.75 mg for the remainder of the treatment period, BMS-986158 will be tested as monotherapy, in a limited set of tumor types (NMC, CRPC, DHL, Non-DC-DLBCL, and TNBC; Initial Expansion).

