#### **4.2.2 Pharmacokinetic Endpoints**

Pharmacokinetics of BMS-986158 monotherapy (parent and metabolite, as data permits) will be derived from plasma concentrations versus time data.

Throughout the SAP, TAU was replaced by 24 hours or 0-24. This is because it is more meaningful to compare PK of first 24 hours following single dose kinetics on cycle 1 day 1, and the dosing interval of 24 hours on cycle 2 NCA (Cycle 2 Day 5 for schedule A, Cycle 2 Day 14 for schedule B and Cycle 2 Day 7 for schedule C). Therefore, with reference to the protocol, the following PK parameters were replaced in the SAP: Ctau was replaced by C24, AUC(TAU) was replaced by AUC(0-24), AI\_AUC(Tau) was replaced by AI\_AUC(0-24), AI\_Ctau was replaced by AI\_C24 and MR\_AUC(TAU) was replaced by MR\_AUC(0-24).

The PK parameters to be assessed following single and multiple dose administration are shown in Tables 4.2.2-1 through 4.2.2-4 below.

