**Table 4.2.2-3: Multi-dose Pharmacokinetic Endpoints**

AI_AUC(0-24)	Accumulation Index; ratio of an exposure measure at steady-state to that after the first dose (exposure measure includes AUC(0-24)).
AI_Cmax	Accumulation Index; ratio of Cmax at steady-state to Cmax after the first dose
AI_C24	Accumulation Index; ratio of an C24 at steady-state to C24 after the first dose
T-HALFeff	Effective elimination half-life that explains the degree of accumulation observed for a specific exposure measure

In addition, the following PK parameters may also be assessed after single and multiple dose administrations, if data permit:

[figure not shown]

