**Figure 7.7.2-1: Effective Half Life**

$$Effective\ T - HALF = \frac{\tau \ln(2)}{\ln\left[\frac{AI}{AI - 1}\right]}, \text{ where } \tau \text{ is the length of one dosing interval in hours, } AI > 1.$$

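### The T-HALFeff formula assumes steady state, but Schedule A is profiled on the fifth daily dose, so its effective half-life reads about 5% to 15% low and is not directly comparable with Schedules B and C

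*SAP*

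**What the plan says.** SAP Table 4.2.2-3 defines the AUC accumulation index (AI) as the "ratio of an exposure measure at steady-state to that after the first dose". SAP 4.2.2 fixes the multiple-dose profile days: "Cycle 2 Day 5 for schedule A, Cycle 2 Day 14 for schedule B and Cycle 2 Day 7 for schedule C". The first-dose exposure comes from the single dose on Cycle 1 Day 1.

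Under SAP 7.7.2, T-HALFeff "will be calculated for Accumulation Index (AI) values of AUC(0-24"). Figure 7.7.2-1 gives the formula T-HALFeff = tau × ln2 / ln[AI/(AI − 1)], where tau "is the length of one dosing interval in hours", that is 24 h for daily dosing.

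On dosing, SAP 2.1 says of Schedule A that "subjects receive QD dosing for 5 consecutive days of each week, followed by a 2-day rest period, on a 28-day cycle". On half-life, SAP Section 1 says: "The rationale for the 3 schedules is based on the human half-life of 39 hours". The only accumulation figure in either document is in Protocol 1.4.4.1, an interim index of about 1.97 from data covering Schedules A and C.

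SAP 7.7.2 and 7.7.3 plot geometric mean Ctrough to look at attainment of steady state. Neither section ties that plot to T-HALFeff by a condition, correction or footnote. The SAP 7.7.2 summaries report T-HALFeff by treatment within each dosing schedule.

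**The concern.** The formula returns the half-life implied by an index measured at steady state. If the index is measured earlier it is too small, and so is the half-life. Five daily doses is a short run for a drug with a stated half-life of 39 h. The shortfall depends on the number of doses before the profile, so it is largest in Schedule A, the schedule taken into Part 2, and smallest in Schedule B.

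At stake is the reading of a secondary PK table. A drug with one effective half-life would show different values by schedule, and the Schedule A value would understate how long accumulation continues.

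**Working it through.** **Inputs.** tau = 24 h (SAP 4.2.2, Figure 7.7.2-1). Doses up to and including the profiled one: n = 5 (A), 7 (C), 14 (B) (SAP 4.2.2). Half-life 39 h (SAP Section 1). Interim AI 1.97 (Protocol 1.4.4.1). The Protocol does not say which exposure measure 1.97 refers to, or how many doses preceded it.

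**What the formula assumes.** Under linear, single-exponential kinetics let r = exp(−ln2 × tau / t½).

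- After n daily doses: AI_n = (1 − r^n)/(1 − r).
- At steady state: AI_ss = 1/(1 − r).
- Fraction of steady state reached: 1 − r^n.

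From AI_ss, AI/(AI − 1) = 1/r, so tau × ln2 / ln[AI/(AI − 1)] = t½ exactly. The SAP formula is therefore correct for AI_ss and too low for any AI_n.

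**Can the documents' own figure be reproduced?** At 39 h, r = exp(−0.6931 × 24/39) = 0.6528. This gives AI_5 = 2.54, AI_7 = 2.73 and AI_ss = 2.88. None matches 1.97, so the size of the bias is worked out under two cases.

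**Case 1: 39 h governs accumulation.** For Schedule A, 1 − 0.6528^5 = 0.8815 and AI_5 = 0.8815/0.3472 = 2.54. T-HALFeff = 16.636/ln(2.539/1.539) = 33.2 h, against 39 h.

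**Case 2: 1.97 is a five-dose, single-exponential value.** Solving (1 − r^5)/(1 − r) = 1.97 gives r = 0.5099, so t½ = 24.7 h, with 96.6% of steady state reached. The SAP formula on 1.97 gives 16.636/ln(1.97/0.97) = 23.5 h. For Schedule C at the same r, AI_7 = 0.9910/0.4901 = 2.022, and the formula gives 24.4 h.

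| Schedule | n | Case 1: fraction of steady state | Case 1: T-HALFeff (bias from 39 h) | Case 2: T-HALFeff (bias from 24.7 h) |
|---|---|---|---|---|
| A | 5 | 88.2% | 33.2 h (−14.8%) | 23.5 h (about −5%) |
| C | 7 | 95.0% | 36.5 h (−6.3%) | 24.4 h (about −1%) |
| B | 14 | 99.7% | 38.9 h (−0.3%) | 24.7 h (negligible) |

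**Variants for Schedule A.**

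- *Carry-over.* Protocol 1.4.4 says: "Each subject was administered a single dose of BMS-986158 on Cycle 1 Day 1 (4- to 7-day cycle"). Adding that dose at 39 h raises AI to between 2.55 (7-day gap) and 2.57 (4-day gap). That is 88.5% to 89.3% of steady state and 33.4 to 33.8 h (−14.4% to −13.4%).
- *Oral absorption.* With an assumed absorption rate constant of 0.5 to 2 per hour, the fraction at 39 h is 87.7% to 88.0%, and T-HALFeff is about 15% below its own steady-state value.
- *Two-phase disposition.* Assume a share f of exposure belongs to a phase complete within 24 h and the rest declines with a 39 h half-life. Matching 1.97 at five doses gives f = 0.169, AI_ss = 1/(0.169 + 0.831 × 0.3472) = 2.19 and a steady-state T-HALFeff of 27.2 h. The SAP formula's 23.5 h is then about 14% low.
- *Later weeks.* With 5 days on and 2 off, even the repeating weekly pattern gives a Day 5 AI of 2.67 at 39 h and T-HALFeff of 35.5 h. Sampling in a later week would not remove the bias.

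The direction is low in every variant.

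**Could a later profile replace Day 5?** No. In Protocol Table 5.5.1-1, the Cycle 2 Day 5 serial samples are followed only by the 24 h sample, two samples on Cycle 2 Day 8 and one in Cycle 4.

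**The case against.** A reader might infer from the 39 h figure that Schedule A's T-HALFeff is simply 15% wrong. The documents do not support that as the expected size. The interim index of 1.97 does not fit a one-compartment 39 h model. T-HALFeff is also defined as the half-life that accounts for observed accumulation, whereas the terminal half-life has its own parameter (T-HALF, SAP Table 4.2.2-2). The two can differ without error, so 39 h is a reference value under one assumption. This objection stands and sets the range at about 5% to 15%.

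A reader might also infer that a finite-dose solve restores the right answer in general. It does so only under single-exponential kinetics with all doses taken. In the two-phase case it returns 24.7 h against 27.2 h, still about 9% low, compared with about 14% low for the current formula. It also ignores the Cycle 1 Day 1 carry-over, and Protocol Section 4 has missed doses skipped, so nominal counts of 5, 7 and 14 will not suit every subject.

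The plan has partial safeguards. The Ctrough plots may show that Day 5 precedes steady state, and Protocol 5.5 foresees population PK modelling of Part 1, which can handle such data. SAP 8.3 defers PK analysis and reporting to a sponsor harmonization document that is not available here, and its treatment of T-HALFeff is unknown. None of this changes the value that the SAP as written would put in the table.

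Finally, no formal between-schedule comparison of T-HALFeff is planned, and Protocol 1.4.4 reports only 8 subjects in Schedule B at the data cutoff. That limits the consequence, although side-by-side tabulation still invites the comparison.

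**Conclusion.** The point holds as a minor one. The formula needs a steady-state index, and the SAP supplies one from the fifth, seventh or fourteenth dose under a steady-state label. In Schedule A this makes T-HALFeff too low, by about 5% if 1.97 is a five-dose, single-exponential value and by up to about 15% if 39 h governs accumulation. In C the bias is about 1% to 6%; in B it is negligible. The direction rests on linear accumulation with increasing exposure over successive doses. The size rests on which half-life drives that accumulation, which the documents do not settle.

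No stronger consequence follows. T-HALFeff is descriptive and enters no decision rule or sample size, and the documents do not suggest that the choice of schedule or dose for Part 2 relied on it.

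**What to change.** 1. In SAP Table 4.2.2-3 and 7.7.2, label each accumulation index by its dosing day (Cycle 2 Day 5, 7 or 14) rather than as steady state.
2. Replace the closed form in Figure 7.7.2-1 with the solution of AI = (1 − r^n)/(1 − r), where r = exp(−k × tau) and n is the number of consecutive doses the subject actually took, up to and including the profiled one. Report T-HALFeff = ln2/k. At 39 h this recovers 39 h from the five-dose AI of 2.54.
3. State that the solve assumes single-exponential disposition, as the current formula also does, and that the small Cycle 1 Day 1 carry-over is ignored.
4. Footnote the table: the Schedule A value may precede steady state and should not be compared directly with B or C.

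The cost is a one-line numerical solve per subject in place of a closed form, plus SAP wording. No added sampling is needed. The downside is residual low bias if disposition is multi-exponential, which is why the footnote should stay even with the solve.
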